Non-operative management of splenic and hepatic injuries has become one of the standards of care in the management of hemodynamically stable patients. Institutional variance exists in management of these injuries regarding serial laboratory values, transfusion thresholds, the utility of interventional radiology/operative management, follow up imaging, and management of delayed findings on this imaging. The delayed complications found both clinically and with follow up imaging vary in the literature from nearly 0% to >15% of cases. There is no clear evidence as to the necessity of repeat imaging or frequency of intervention in blunt splenic and hepatic injuries. Some studies recommend only follow up

imaging for high grade injuries, whereas other studies have found no correlation between grade of injury and complications.

Our group approached this question through a dual institution, retrospective pilot study observing the management of delayed splenic and hepatic complications found on repeat imaging. This study was performed in the adult population and a current study is ongoing in the pediatric population. Imaging was obtained either via the institutions standard protocol (SP) or physician discretion (PD) (lab or vital sign abnormalities, clinical change, etc). There were 235 splenic injuries with 45% undergoing repeat imaging. 64% of these were due to PD. Complications were found in 47% of SP and 42% of PD patients (p=0.683). Interventions performed for these complications was done for 56% SP v. 21% of PD patients (p=0.027). This pilot study suggested that patients with blunt splenic injuries should undergo repeat imaging for delayed complications and that those who underwent repeat imaging by SP had complications identified sooner (2.4 v 4.4 days) and treated earlier than the PD group.

Of the 365 liver injuries, 33.4% underwent repeat imaging with a majority (59%) of these due to physician discretion. Complications were found in 20% of SP patients and 27% of PD patients (p=0.395). Interventions were performed in 20% SP v. 25% PD patients that had complications (p=1.00). In the liver injury group there was no difference found between complications or interventions performed when assessed by SP or PD; waiting to perform repeat imaging based on PD could prevent unnecessary imaging in blunt liver injuries.

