Categorical variables will be compared using Fisher's exact test or Chi-squared test. Continuous variables will be assessed using Student's t-test. For multivariate analysis, a mixed effect multinomial logistic regression will be run with a binary outcome of whether the patient had a delayed complication. Another mixed effect multinomial logistic regression will be run with a binary outcome of whether the patient had an intervention performed. Additional analysis will be completed to determine if there is optimal timing for repeat imaging to identify complications. Data will be reported as adjusted odds ratios with 95% confidence intervals. Statistical significance will be defined by a p<0.05.

Sample Size and Power Estimates

A retrospective pilot study was completed with 235 patients with splenic injuries and 365 hepatic injuries. Of the patients with splenic injuries, 105 underwent repeat imaging, 46 had organ specific complications, and 16 had an intervention performed. Of the patients with hepatic injuries, 122 underwent repeat imaging, 30 had organ specific complications, and 12 had an intervention performed.

Spleen Power Analysis

Combined complication rate for patients who had repeat imaging: 46/105 = 0.44Standard protocol complication rate: 18/38 = 0.47Physician discretion complication rate: 28/67 = 0.42

Complication Rate:	Complication Rate:	Odds Ratio	Sample Size
Standard protocol	Physician discretion		(Total Population)
0.46	0.43	0.89	8,614
0.47	0.42	0.82	3,100
0.48	0.41	0.75	1,582

Liver Power Analysis

Combined complication rate for patients who had repeat imaging: 30/122 = 0.25Standard protocol complication rate: 10/50 = 0.20Physician discretion complication rate: 20/72 = 0.27

Complication Rate: Standard protocol	Complication Rate: Physician discretion	Odds Ratio	Sample Size (Total Population)
0.21	0.26	1.32	2,256
0.20	0.27	1.48	1,150
0.19	0.28	1.66	696

Consent Procedures

This is a retrospective observational study in which data will be retrospectively recorded on patients according to institutional protocols. Data will be input into REDcap database without any patient identifiers. Thus, a waiver of consent is requested.

Confidentiality and Privacy

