Admission Anticoagulation/Antiplatelet	Yes/No dropdown menu. Yes = patient on anticoagulation and/or antiplatelet therapy at time of admission. No = no anticoagulation or antiplatelet therapy at time of admission.
Anticoagulation/Antiplatelet Agent	If yes checked for Admission Anticoagulation/Antiplatelet, description of anticoagulation/antiplatelet agent which was present on admission. Check all that apply:
	Warfarin Rivaroxaban Apixaban Dabigatran Aspirin Clopidogrel Ticagrelor Other
Reversal Agents Given	Yes/No dropdown menu. Yes = reversal for anticoagulation given. No = no reversal agents given.

Admission Anticoagulation and Reversal (continued)

Reversal Agent	If yes checked for Reversal Agents Given, description of reversal agents used. Check all that apply:
	K centra Andexanet Idarucizumab Vitamin K FFP Other
Patient History of Coagulopathy	Yes/No dropdown menu. Yes = Patient with history of coagulopathy on admission. No = Patient with no history of coagulopathy on admission.
Initial INR	Numerical value for patient's INR on admission. (INR = International Normalized Ratio)
Initial Imaging	
Initial FAST	Single choice for initial Focused Assessment with Sonography for Trauma (FAST). Options include:
	Yes: FAST performed on initial assessment, results not available.
	Yes/positive: FAST performed on initial assessment and positive defined by fluid present in at least one of four views.
	Yes/negative: FAST performed on initial assessment and negative defined by no fluid present in any of the four views.
	No: FAST not performed on initial assessment.
Area of FAST positive	If Yes/positive checked for Initial FAST, description of area of FAST which is positive. Check all that apply:
	Pericardial Right Upper Quadrant Left Upper Quadrant Suprapubic
Initial CT	Single choice for initial computed tomography (CT) scan of the abdomen/pelvis. Options include:
	Yes: CT scan performed on initial assessment.
	No: CT scan not performed on initial assessment.
	After emergent operating room (OR): CT scan performed after patient

Initial Imaging (continued).

Organs Injured	Single choice for organ injuries identified on initial CT scan or within OR if occurred before imaging. Options include:
	Liver: Hepatic injury of any grade present on initial CT scan or found in OR at initial emergent operation.
	Spleen: Splenic injury of any grade present on initial CT scan or found in OR at initial emergent operation.

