First Repeat Imaging Hours from Admission	If yes checked for First Repeat Imaging, numerical value for when repeatimaging was performed in hours from admission.
Reason for First Repeat Imaging	If yes checked for First Repeat Imaging, single choice for best reason for scan. Options include:
	Clinical Change: Repeat imaging prompted by patient factors including, but not limited to, vital sign changes, lab abnormalities, abdominal pain, and patient symptoms.
	Non-Clinical Change: Repeat imaging prompted by institutional protocol/recommendations, individual physician practice pattern, or that performed on a scheduled basis.
First Repeat Imaging Findings	If yes checked for First Repeat Imaging, free text of organ specific (hepatic or splenic) imaging findings.
Organ Specific Delayed Complication	tions
Liver Complications	Liver specific complications found during hospital admission. Check all that apply. Options include:
	Increased bleeding, including increased hemoperitoneum. Pseudoaneurysm Hemobilia New area of hepatic injury not previously recognized on initial workup. Hepatic infarct (not post-IR/post-intervention). Abscess Fulminant liver failure Bile leak/biloma Unexpected thrombosis (of hepatic and related vessels) Need for OR/intervention other than initial Other (free text)

Organ Specific Delayed Complications (continued)

Spleen Complications	Spleen specific complications found during hospital admission. Check all that apply. Options include:
	Increased bleeding, including increased hemoperitoneum. Pseudoaneurysm Delayed rupture. New area of splenic injury not previously recognized on initial workup. Splenic infarct (not post-IR/post-intervention). Abscess Unexpected thrombosis (of splenic and related vessels) Pancreatic fistula Arteriovenous fistula Need for OR/intervention other than initial Other (free text)
Intervention Information	
Initial Intervention	Intervention for hepatic and/or splenic injury prior to repeat imaging (can occur post-initial imaging assessment). Yes/No dropdown menu. Yes = intervention performed for hepatic and/or splenic injury at initial assessment, prior to repeat imaging. No = no intervention performed for hepatic and/or splenic injury at initial assessment, prior to repeat imaging.
Initial Intervention Timing	If yes checked for Initial Intervention, numerical value for time to intervention from presentation (in hours).

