Initial Intervention Type	If yes checked for Initial Intervention, single best choice for type of intervention performed. Options include:
	OR: Patient taken to operating room.
	Damage Control: Operation specifically described as damage control or patient described as unstable.
	Planned OR: Operation on stable patient.
	Interventional Radiology (IR): Patient taken to IR suite for intervention.
	Other
Initial Intervention Description	If yes checked for Initial Intervention, free text briefly describing organ specific (hepatic or splenic) intervention.
Post-Imaging Intervention	Intervention for hepatic and/or splenic injury following repeat imaging (as a result of the imaging findings). Yes/No dropdown menu. Yes = intervention performed for hepatic and/or splenic injury following repeat imaging. No = no intervention performed for hepatic and/or splenic injury following repeat imaging.
Post-Imaging Intervention Timing	If yes checked for Post-Imaging Intervention, numerical value for time to intervention from presentation (in hours).

Intervention Information (continued)

	_
Post-Imaging Intervention Type	If yes checked for Post-Imaging Intervention, single best choice for type of intervention performed. Options include:
	OR: Patient taken to operating room.
	Interventional Radiology (IR): Patient taken to IR suite for intervention.
	Other
Post-Imaging Intervention Description	If yes checked for Post-Imaging Intervention, free text briefly describing organ specific (hepatic or splenic) intervention.
Intervention Complication	Complications of organ specific (hepatic or splenic) interventions which occurred during the hospitalization. Check all that apply. Leave blank if no complications of interventions found.
	Migration of coil Rupture of vessel Pancreatic fistula post-splenectomy Abscess
	Need for repeat intervention/surgery Other (free text)
Transfusion Information	
Transfusions	Yes/No dropdown menu for transfusions during hospital admission. Yes = patient received blood products (whole blood, pRBCs, FFP, platelets) during hospital admission. No = patient did not receive blood products during hospital admission.
4h Whole Blood Total Units	Total units of Whole Blood administered in the first 4 hours (4h) from presentation.
4h pRBC Total Units	Total units of Packed Red Blood Cells (pRBC) administered in the first 4 hours (4h) from presentation.

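### The study is sized by organ on opposite planning effects, but the two main regressions are written per patient with no organ split or organ-by-imaging interaction

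*Supplement*

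**What the plan says.** Under Data Collection and Statistical Analysis there are two main regressions. In the first, "a mixed effect multinomial logistic regression will be run with a binary outcome of whether the patient had a delayed complication". The second reads: "Another mixed effect multinomial logistic regression will be run with a binary outcome of whether the patient had an intervention performed". Both outcomes belong to the patient. Neither sentence names an organ, an organ covariate or an interaction.

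The sample size is by organ: 3,500 splenic plus 1,500 hepatic injuries, with separate spleen and liver power tables. The central rows compare standard protocol (SP, now non-clinical change) with physician discretion (PD, now clinical change): 0.47 v 0.42 for spleen (OR 0.82) and 0.20 v 0.27 for liver (OR 1.48).

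The Background draws organ-specific conclusions from the pilot. It favours repeat imaging for spleen; for liver it says that "waiting to perform repeat imaging based on PD could prevent unnecessary imaging in blunt liver injuries".

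The Data Dictionary lists complications separately for liver and spleen. Organs Injured is a "Single choice for organ injuries identified on initial CT scan or within OR if occurred before imaging", with a category for both organs. Each in-hospital intervention item covers both organs in one answer: the initial item is "Intervention for hepatic and/or splenic injury prior to repeat imaging (can occur post-initial imaging assessment). Yes/No dropdown menu" and the later one is "Intervention for hepatic and/or splenic injury following repeat imaging (as a result of the imaging findings). Yes/No dropdown menu". Each has a description field, "free text briefly describing organ specific (hepatic or splenic) intervention".

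**The concern.** If the organ effects run in opposite directions, as the power tables assume, one patient-level odds ratio averages them towards no effect. The average also depends on how many splenic and hepatic injuries the sites contribute, which a chart review of all blunt injuries does not control. Aims 1 to 3 ask which splenic and hepatic injuries are at risk and which patients need imaging and intervention. A pooled null could not answer that, and it could be misread as showing that the reason for imaging does not matter. The analysis section also does not say how a patient with both organs injured enters the models.

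**Working it through.** **Inputs.** The rates, pilot counts and 3,500:1,500 mix come from the power and analysis sections. The plan gives p<0.05 but not sidedness, power or allocation.

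**1. Reproduce the plan's figures.** With two-sided 5%, 80% power, 1:1 groups and p̄ = (p1+p2)/2:

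n per group = [1.96·√(2p̄(1−p̄)) + 0.842·√(p1(1−p1)+p2(1−p2))]² / (p1−p2)²

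- Spleen 0.47 v 0.42: n = 1,549.6, rounded up to 1,550; total 3,100, as stated.
- Liver 0.20 v 0.27: n = 574.8, rounded up to 575; total 1,150, as stated.

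The other four rows also match (8,614; 1,582; 2,256; 696), so these settings are a sound inference. The ORs match as PD v SP.

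**2. Power by organ at the planned size** (1:1, all assumed imaged, m per group):

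power = Φ{[|p1−p2|·√m − 1.96·√(2p̄(1−p̄))] / √(p1(1−p1)+p2(1−p2))}

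- Spleen, m = 1,750: (2.092 − 1.377)/0.702 = 1.02, so 85%.
- Liver, m = 750: (1.917 − 1.175)/0.598 = 1.24, so 89%.

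**3. Pooled, as the models are worded** (m = 2,500)

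- SP: 0.7×0.47 + 0.3×0.20 = 0.389.
- PD: 0.7×0.42 + 0.3×0.27 = 0.375.
- OR = (0.375/0.625)/(0.389/0.611) = 0.94.
- Power: (0.700 − 1.347)/0.687 = −0.94, so 17%.

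**4. Organ as a main effect only.** The log ORs are −0.203 (variance 0.00464) and 0.392 (variance 0.01510). The inverse-variance mean is −0.063 (SE 0.060), giving a common OR of 0.94 and about 18% power. The organ-by-imaging interaction has z = (0.203 + 0.392)/√(0.00464 + 0.01510) = 4.23, about 99% power.

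**5. Sensitivity**

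| Setting | Spleen power | Liver power | Pooled OR | Pooled power |
|---|---|---|---|---|
| 3,500:1,500, 1:1 | 85% | 89% | 0.94 | 17% |
| Same, pilot SP:PD splits (38:67, 50:72) | 82% | 88% | 0.98 | about 6% |
| 2,500:2,500, 1:1 | 71% | 98% | 1.05 | 11% |
| 5,000 at the pilot's re-imaged mix, 105:122, 1:1 | 68% | 99% | 1.07 | 19% |
| Only pilot fractions imaged (3,500×105/235 = 1,564; 1,500×122/365 = 501), 1:1 | 51% | 46% | 0.92 | 16% |

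The pooled OR crosses 1 as the mix shifts towards liver.

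**6. Pilot data**

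- Complications, PD v SP: spleen OR (28/39)/(18/20) = 0.80; liver OR (20/52)/(10/40) = 1.54. Pooled, 28/88 v 48/139 (SP v PD) gives OR 1.13. Interaction p = 0.27.
- Interventions among complications, SP v PD, with counts derived from the stated percentages: spleen 10/18 v 6/28, Fisher p = 0.027; liver 2/10 v 5/20, p = 1.00; pooled 12/28 (43%) v 11/48 (23%), p = 0.077. The derived splenic total (16) matches the plan. The derived hepatic total (7) does not match the stated 12, so the pooled p-value is illustrative.

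**The case against.** **Pooling is inferred from silence.** The separate power tables, the split by organ, the organ-specific complication items and a pilot reported by organ all suggest that organ-level analysis may be intended. The model sentences could describe a regression run within each organ cohort. This stands: the plan does not say that it will pool. But it does not say the reverse either, on the choice that decides its power.

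**The pilot did not show opposite effects.** A reader might infer that it did. The complication differences had p = 0.683 and 0.395, the interaction p is 0.27, and the Background itself reports no difference for liver. The spleen recommendation also leans on earlier detection (2.4 v 4.4 days). This stands too. The directions are point estimates, but the sample size is built on them.

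**The intervention outcome is diluted, not reversed.** Pooled pilot interventions remain 43% v 23%. Near-cancellation is shown for complications only.

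**The form holds more organ detail than the intervention items suggest.** A reader might infer that only free text identifies the treated organ, or that a second intervention on the other organ has no coded place. The documents do not support that. The liver and the spleen complication lists each carry a tick for an operation or intervention beyond the initial one. For patients with one injured organ, Organs Injured settles the matter. What lacks coding is the organ of the initial intervention, and a separate time and type per organ, in patients with both injuries. Their share is not given.

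**Conclusion.** The concern holds as a gap in the model specification. On the plan's own planning rates, per-patient models without an organ-by-imaging interaction would have about 17% power for complications (about 6% at the pilot's SP:PD splits), against about 85% and 89% by organ. The pooled OR of 0.94 describes neither organ, and its direction depends on case mix. Pooling would also dilute the pilot's one significant intervention contrast, from p = 0.027 to about 0.077 on derived counts.

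The power levels assume 1:1 groups, every patient imaged, no patient counted in both organs and no clustering by site. Imaging at the pilot's fractions lowers power by organ to about 51% and 46%, still well above the pooled 16%. The conclusion does not require the opposite effects to be real, only that the analysis should be able to test what the study was sized for. The data form is a minor matter, because complications can already be separated by organ.

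**What to change.** In the analysis section:

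- Define the complication and intervention outcomes per organ: any splenic event among patients with a splenic injury, and any hepatic event among patients with a hepatic injury.
- Fit each regression separately in the two groups. Alternatively, fit one model with an organ-by-imaging interaction and clustering within patient and site.
- State that patients with both injuries contribute each organ's own outcome to that organ's analysis.
- Keep the combined per-patient outcome as descriptive.
- For patients with both injuries, assign later interventions to an organ from the existing organ-specific tick and the description field.

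An organ tick on the initial and post-imaging intervention items is an optional addition for records not yet abstracted.

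The required change is a few sentences and no new data. The price is fewer events per model than in a pooled one. That is acceptable, since the study is already sized by organ. The optional tick adds a little abstraction work; extending it to completed records would mean going back to the sites.

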In this small pilot study we were unable to achieve all of our primary and secondary endpoints. Additionally, interventions in low grade injuries are uncommon, and a larger data set would allow for delineation in management between low, moderate and high grade splenic and hepatic injuries. This study did not have power due to a limited number of patients receiving interventions, thus making characterization of types of interventions and final outcomes difficult.

A large multicenter trial would allow for appropriate power for the study and thus allow for us to meet our endpoints. There are multiple variables affecting the management of blunt splenic and hepatic injuries and currently no clear guidelines exist in regards to repeat imaging. Gaining a better understanding of types of delayed complications, how they present, and current management strategies would assist in creating a standardized algorithm in the treatment of this patient population.

Specific Aims of Multicenter Study

Aim 1: To define which blunt splenic and hepatic injuries are at risk of delayed complications in order to develop a societal management guideline.

Aim 2: To ascertain which patients warrant repeat imaging and when this imaging should be performed.

Aim 3: To define what interventions are needed based upon delayed complications found radiographically.

Aim 4: To analyze 30 day readmission rates to the hospital due to spleen and/or liver injury.

Methods

This will be a retrospective observational study. Patients will be managed according to the surgeon's discretion. The study will enroll a total of 5,000 subjects at minimum. This study plans to enroll 200 patients at our institution, Penn Medicine Lancaster General Health. The number of subjects that will be enrolled at each additional participating site is 200.

Inclusion Criteria:

• All patients (all ages) who present with blunt trauma to the spleen and/ or liver

Exclusion Criteria:

- Patients who suffer a penetrating mechanism
- Patients transferred out to another facility prior to admission

Updated Terms/Definitions:

• **Clinical Change (CC) (to replace Physician Discretion)**- repeat imaging prompted by patient factors including vital sign changes, lab abnormalities, abdominal pain, and patient symptoms

• Non Clinical Change (NCC) (to replace Standard Protocol)- repeat imaging prompted by institutional protocol/ recommendations, individual physician practice pattern, or that performed on a scheduled basis

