The time frame for data query will be from IRB approval (2020) until December 31, 2023. The electronic medical record (EMR) may be used in order to identify participants who match study defined demographic criteria.

Primary Outcome: Delayed complications found on repeat imaging

Secondary Outcomes: Timing to repeat imaging/ intervention, interventions performed based on complications found, mortality, length of stay, blood transfusion requirements, VTE prophylaxis, and 30 day readmission variables [readmission within 30 days for spleen and/or liver injury, readmission CT scan, interventions performed].

Variables

List specific variables to be collected & analyzed: Age, sex, time from injury, Injury Severity Score (ISS), Abbreviated Injury Scale (AIS), Trauma and Injury Severity Score (TRISS), mechanism of injury, initial vital signs, anticoagulant use and reversal agents, initial and repeat imaging, grade of organs injured, complications found, details regarding initial and any delayed interventions, blood transfusions, details regarding venous thromboembolism prophylaxis, venous thromboembolism complications, hospital length of stay, intensive care unit length of stay, mortality, and 30 day readmission variables [readmission within 30 days for spleen and/or liver injury, readmission CT scan, interventions performed].

Data Collection and Statistical Analysis

Standardized data will be collected for each patient meeting inclusion criteria (see data collection tool). The de-identified data for each patient will be entered into a secure REDCap database. A total of 5,000 patients (3,500 splenic injuries and 1,500

hepatic injuries) is recommended to identify a significant difference between the non clinical change and clinical change group. Complications found on repeat imaging will be assessed using univariate and multivariate analysis.

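### The liver power table is centred on a misprinted pilot rate: 20/72 is 0.278, not 0.27, so the middle row (OR 1.48, total 1,150) is not the row for the pilot's liver counts

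*Supplement*

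**What the plan says.** The Sample Size and Power Estimates section takes its planning rates from a two-institution pilot. For the liver it gives 30 complications in 122 re-imaged patients overall, 10/50 = 0.20 in the standard-protocol group, and for the physician-discretion group "complication rate: 20/72 = 0.27". The liver table has three rows: 0.21 v 0.26 (OR 1.32, total 2,256), 0.20 v 0.27 (OR 1.48, total 1,150) and 0.19 v 0.28 (OR 1.66, total 696). The middle row uses the two rates printed just above the table, and the outer rows move each rate by 0.01.

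Background & Significance carries the same figure: "Complications were found in 20% of SP patients and 27% of PD patients (p=0.395").

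For the spleen, the corresponding entry is "complication rate: 28/67 = 0.42", set against 18/38 = 0.47, with a middle row of 0.47 v 0.42 (OR 0.82, total 3,100).

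The Data Collection and Statistical Analysis section then recommends "A total of 5,000 patients (3,500 splenic injuries and 1,500" hepatic). On significance, the protocol says "Statistical significance will be defined by a p<0.05". It gives no sidedness, no power figure and no allocation ratio for the tables.

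**The concern.** The equation printed for the liver physician-discretion group is false. The value has been cut off at the second decimal rather than rounded, and it is the only one of the four group rates printed wrongly.

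It matters beyond a typing slip because the middle liver row uses that rate and the outer rows are stepped from it. Required size varies roughly with one over the squared difference between the rates. Moving the difference from 0.0778 to 0.07 therefore changes the total noticeably. The liver rate of 0.28, which is the pilot's own rounded value, appears only in the most favourable row, paired with 0.19.

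These tables are the only quantitative support shown for the recommended numbers. A reader who starts from the stated counts cannot reproduce the middle liver row.

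**Working it through.** **1. Is the count or the decimal wrong?**
- 20/72 = 0.2778, which rounds to 0.28.
- The counts add up: 10 + 20 = 30 and 50 + 72 = 122, matching the combined 30/122 in the same section.
- Fisher's exact test on 10/50 v 20/72 gives p = 0.395, the value in the background. With 19/72 it would be 0.518.
- So 20/72 is right, and 0.27 and 27% are wrong.
- The other three rates are correct to two decimals: 18/38 = 0.474, 28/67 = 0.418, 10/50 = 0.200.

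**2. Reproduce the printed tables.**

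With p̄ = (p1 + p2)/2, the size per group is

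n = [1.960 × √(2p̄(1 − p̄)) + 0.8416 × √(p1(1 − p1) + p2(1 − p2))]² / (p1 − p2)²

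n is rounded up, and the total is 2n. The settings are two-sided 0.05, 80% power, 1:1 and no continuity correction. All are inferred, except that the 0.05 level is stated.

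- Spleen: 8,614 / 3,100 / 1,582, all as printed.
- Liver: 2,256 / 1,150 / 696, all as printed.

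For the middle liver row (0.20 v 0.27), p̄ = 0.235 and the two square roots are 0.5996 and 0.5976. This gives n = 574.8, rounded up to 575, total 1,150. The formula was applied correctly; the input is at fault.

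**3. Recompute the liver rows.**

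From the counts (0.2000 v 0.2778), p̄ = 0.2389 and the square roots are 0.6030 and 0.6005. This gives n = 470.6, rounded up to 471, total 942. OR = (20/52)/(10/40) = 1.54.

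| Liver rates | OR | Total |
|---|---|---|
| 0.20 v 0.27 (printed) | 1.48 | 1,150 |
| 10/50 v 20/72 (counts) | 1.54 | 942 |
| 0.20 v 0.28 (correctly rounded) | 1.56 | 894 |
| 0.21 v 0.27 (one step narrower than 0.20 v 0.28) | 1.39 | 1,590 |
| 0.19 v 0.29 (one step wider than 0.20 v 0.28) | 1.74 | 572 |

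1,150/942 = 1.22, so the printed total is 22% above the size from the counts. Taking the printed total as base, the correction is −18%.

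**4. Sensitivity to the inferred settings.** For the liver counts, a continuity correction at 1:1 gives 994. The pilot's own split (50:72) without the correction gives 981. Both are still below 1,150.

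**5. Power at the recommended 1,500 liver patients** (same formula solved for power, 750 per group, all analysable):
- at 0.20 v 0.27: 89%
- at 10/50 v 20/72: 94%

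**6. Spleen, for comparison.** From the counts (18/38 v 28/67) the total is 2,492 and the OR is 0.80, against 3,100 and 0.82 printed. The gap comes only from correct two-decimal rounding of a small difference (0.0558 becomes 0.05).

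**The case against.** The best defence is that nothing in the design turns on this. Each row states its own assumed rates, and its total and odds ratio are right for those rates. The exact liver difference (0.0778) lies between the 0.07 and 0.09 rows, so 942 falls inside the printed range of 1,150 to 696. The recommended 1,500 exceeds every version of the middle total.

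The pilot difference is also very imprecise. Its standard error is √(0.20 × 0.80/50 + 0.2778 × 0.7222/72) = 0.077, so the 95% interval runs from about −7 to +23 points. A shift of 0.8 points is small beside that. The recomputed totals also rest on power and allocation that the protocol does not state.

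All of this stands, and it sets the severity. It does not rescue the printed equation, which is simply false, or make 0.27 the right centre for a table presented directly under the pilot counts.

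A reader might infer that the spleen table is wrong as well, because unrounded counts give 2,492 rather than 3,100. The documents do not support that. Both spleen rates are correctly rounded, and planning on two-decimal rates is ordinary practice. The total of 3,100 and OR of 0.82 are right for the rates printed beside them.

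**Conclusion.** One pilot rate is misprinted in two places, and the liver table is centred on it. From the pilot counts, the middle liver row should read about 942 with OR 1.54 (894 with OR 1.56 at 0.28), not 1,150 with OR 1.48. The misprint itself is certain from the documents. The replacement totals assume 80% power, a two-sided test and 1:1 allocation, inferred because they reproduce all six printed rows.

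The error is conservative and costs no power, so severity is low. A reader might go further and infer that the study is mis-sized or that enrolment could be reduced. Neither follows. The recommended figures already exceed the middle totals. The 94% power holds only if all 1,500 liver patients enter the comparison, and it takes an imprecise pilot estimate at face value.

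**What to change.** - In Liver Power Analysis, change 0.27 to 0.28 for 20/72. In Background & Significance, change 27% to 28%.
- Recompute the liver rows from 10/50 and 20/72 (middle row about 942, OR 1.54). If two-decimal rates are kept, use 0.21 v 0.27 (1,590), 0.20 v 0.28 (894, OR 1.56) and 0.19 v 0.29 (572).
- State the power, sidedness and allocation behind both tables, so that a reader can reproduce them.
- Leave the 3,500 and 1,500 targets as they are.
- Optionally, show the spleen row from its counts (2,492, OR 0.80) as a refinement.

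The cost is two corrected figures, one recalculated table and a sentence of settings. No patients, data items or analyses change.
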